## **6.2 Preexisting Condition**

A preexisting condition is one that is present at the start of the study. A preexisting condition should be recorded as an adverse event if the frequency, intensity, or the character of the condition worsens during the study period.

At screening, any clinically significant abnormality should be recorded as a preexisting condition. At the end of the study, any new clinically significant findings/abnormalities that meet the definition of an adverse event must also be recorded and documented as an adverse event.

## **6.3 Post-study Adverse Event**

All unresolved AEs will be followed by the study team until the events are resolved, the subject is lost to follow-up, or the AE is otherwise explained. A review of AEs which the subject or subject's physician believe might reasonably be related to participation in the study will be performed up to 12 months following surgery.

## **6.4 Hospitalization, Prolonged Hospitalization or Surgery**

Any AE related to the study intervention that results in hospitalization or surgery should be documented and reported as a serious AE.

Neither the condition, hospitalization, prolonged hospitalization, nor surgery are reported as an adverse event in the following circumstances:

- Hospitalization or prolonged hospitalization for diagnostic or elective surgical procedures for a preexisting condition. Surgery should not be reported as an outcome of an adverse event if the purpose of the surgery was elective or diagnostic and the outcome was uneventful.

## **6.5 Recording of Adverse Events**

The study team will seek information on adverse events by specific questioning between baseline and the 3 month visit. Information on all adverse events will be recorded immediately in the adverse event section of the specific questionnaire as well as in an adverse event form (see Attachment – Adverse Event Form).

All adverse events occurring during the study period will be recorded. The clinical course will be followed until resolution, stabilization, or until it has been ultimately determined that the study treatment or participation is not the probable cause. Serious adverse events that are still ongoing at the end of the study period will be followed up, to determine the final

outcome. Any serious adverse event that occurs after the study period and is considered to be at least possibly related to the study treatment or study participation will be recorded and reported immediately.

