### **3.5 Study Schema**

During the initial scheduled clinic appointment, the patient will receive a description of the study, and informed consent. Potential subjects will be notified about the two groups for the study: Treatment (PTT for 30 min 3x/day for 3 months) or No Treatment (control). Subjects planning to have their IPP procedure immediately and do not want to utilize traction therapy will be considered for the control group. Subjects who wish to wait for placement of IPP and are interested in utilizing traction will enter into the treatment group. Those consenting will receive initial study assessments and subjects who take part in the treatment group will be educated on how to use the device properly.

Patients will then be given a baseline questionnaire to complete and, if assigned to the treatment group, begin using the device. Patients in the treatment arm will record a daily journal of their usage of the device.

After 3 months (+1.5 months permitted), patients in the treatment arm will return for their scheduled procedure (control arm patients will undergo surgery without a 3-month delay). Only those who utilized the device for 3 months will be asked to complete a follow-up questionnaire at this time. Patients will also be encouraged to self-report any additional adverse events (AE's) that they encountered over the 3 months of using the therapy.

During surgery, data will be recorded by the surgeon to indicate type, length and approach taken for penile prosthesis implanted as well as any complications of penile prosthesis implantation. These complications may include urethral perforation, corporal perforation, device malfunction, bowel injury or vascular injury; all of which are standard potential complications of the surgery.

Following surgery, patients will be seen in the clinic based on the standard routine clinical practice. During these follow-up appointments, penile length measurements will be performed and recorded.

Patients will also be sent questionnaires by email or by mail (if email not available) at 3, 6, and 12 months post-operatively. If a patient has not returned their questionnaire within 2 weeks, a follow up phone call to the patient will be placed as a reminder. Alternatively, patients may answer the questions over the phone if that method is preferable.

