### 4.2 Follow-up Visit – Treatment Group

- Questionnaire after penile traction, but before IPP surgery

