#### **4.6 Schedule of Events**

**Table 1: Schedule of Events for Treatment Group**

Study Activity	Baseline	3 Month	6 Month (3 months post-op)	9 Month (6 months post-op)	15 Month (12 months post-op)
Consent	X				
Baseline Questionnaire	X				
Length Assessment	X				
Patient Diary Provided	X				
PTT Experience Questionnaire		X			

Penile Prosthesis Implanted		X			
Penile Prosthesis Length Recorded		X			
PP Follow-Up Questionnaire			X	X	X
Chart Review of Post-Op Complications					X

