### 5.2 Statistical Analysis

Analyses will be performed using comparisons within patients of same baseline penile stretch length and between groupings of varying lengths. Comparison of device length implanted will be made for subjects using the traction device compared to those who did not utilize traction. Comparisons will also be made on other subjective and objective variables obtained including number of adverse events, complications, subjective responses to questionnaires, or other information. Pre- and post-operative penile lengths will also be compared within individuals. All data will be normalized based on pre-operative stretched penile length.

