### 6.1 Adverse Event Reporting Period

For the current study, the treatment follow-up period is defined as 3 months following implantation of the penile prosthesis.

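### Section 6.5 does not tie adverse-event questioning to surgery, so the adverse-event counts compared in section 5.2 mix traction-phase with post-operative events

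*Combined protocol and SAP*

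**What the plan says.** Three sections bear on when AEs are sought and how they are compared.

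- Section 6.5, on active questioning: "The study team will seek information on adverse events by specific questioning between baseline and the 3 month visit". It adds that every AE in the study period is to be recorded, and mentions an AE section in a questionnaire without saying which one.
- Section 6.1, on the reporting period: "For the current study, the treatment follow-up period is defined as 3 months following implantation of the penile prosthesis".
- Section 5.2, on analysis: "Comparisons will also be made on other subjective and objective variables obtained including number of adverse events, complications". It gives no window, time origin or phase for the AE comparison.

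The arms reach surgery at different times. Section 3.5 says of treated men: "After 3 months (+1.5 months permitted), patients in the treatment arm will return for their scheduled procedure". Of controls it says: "control arm patients will undergo surgery without a 3-month delay". Table 1 puts implantation in the month-3 column and labels the next contact "6 Month (3 months post-op)". Table 2 puts implantation in the baseline column, so its month-3 column is 3 months after surgery.

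Section 4.2 lists one assessment at the end of traction: "Questionnaire after penile traction, but before IPP surgery". Section 3.5 restricts it: "Only those who utilized the device for 3 months will be asked to complete a follow-up questionnaire at this time".

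**The concern.** A visit named only by its month means different things in the two arms, because surgery comes at the start for controls and after traction for treated men. If section 6.5 follows the schedule tables, treated men are questioned up to the operation and controls after it. If it means the end-of-traction visit, controls are not questioned at all under that sentence. Either way, the AE counts in section 5.2 would come from different stages of care and different efforts to find events.

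What is at stake is a secondary safety comparison. A difference between arms could reflect who was asked, and when. Equally, traction-phase effects could be added to post-operative events in one arm only, so that the total answers neither the question about the device (secondary objective 3) nor the question about post-operative safety.

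**Working it through.** The plan gives no figure to reproduce, so the check lays each arm's windows on a time axis.

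**Inputs**
- Surgery in controls: month 0 (Table 2; section 3.5).
- Surgery in treated men: month 3, up to 3 + 1.5 = 4.5 (Table 1; section 3.5).
- End of the section 6.1 period: surgery + 3 months. This is 0 + 3 = month 3 in controls, and 3 + 3 = 6 to 4.5 + 3 = 7.5 in treated men.
- Men per arm: 40 accrued, with a minimum of 20 completing (section 3.4).

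**Three readings of the month-3 visit in section 6.5**
- A: the visit in the month-3 column of each schedule table.
- B: the treated arm's end-of-traction visit.
- C: 3 months after implantation in both arms.

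Post-operative months questioned = end of questioning minus time of surgery, and not below zero. Traction months questioned = time from baseline to surgery in treated men, and zero in controls.

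- A, controls: 3 − 0 = 3 post-operative months, or fewer if surgery lags baseline. A, treated: 3 − 3 = 0, or 4.5 − 4.5 = 0 if the visit is late.
- B: no control is questioned, and treated men are questioned only up to surgery.
- C, controls: 3 − 0 = 3. C, treated: 6 − 3 = 3, or 7.5 − 4.5 = 3.

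| Reading | Post-op months per man, control / treated | Traction months per man, control / treated | Post-op person-months at 40 per arm, control / treated |
|---|---|---|---|
| A | up to 3 / 0 | 0 / 3 to 4.5 | 40 × 3 = 120 / 0 |
| B | 0 / 0 | 0 / 3 to 4.5 | 0 / 0 |
| C | 3 / 3 | 0 / 3 to 4.5 | 120 / 120 |

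Traction person-months, treated arm only: 40 × 3 = 120 to 40 × 4.5 = 180. At 20 completers per arm every person-month figure halves: 60 in place of 120, and 60 to 90 for traction.

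The post-operative column depends on the reading. The traction column does not. Even under C, the most favourable reading, a treated man is questioned for 3 + 3 = 6 to 4.5 + 3 = 7.5 months against 3 for a control. That is 6/3 = 2 to 7.5/3 = 2.5 times as long.

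**Other capture**
- Surgeons record intra-operative complications, and post-operative visits note complications and AEs, in both arms (section 4.3). Those visits follow each surgeon's own schedule.
- Records are reviewed to 12 months after surgery for revision, infection and hospitalization in both arms (sections 3.5 and 4.4).
- The review to 12 months in section 6.3 covers only AEs thought related to study participation. Controls receive no study device, so it does little for them.
- AE forms carry dates (section 6.6.1). Recorded events can therefore be split by phase afterwards, but events that surface only on asking cannot be recovered.

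**The case against.** The strongest reply is that section 6.5 means reading B. Controls have no protocol-defined clinic visit at month 3: their contact then is a survey or a telephone call. The only scheduled month-3 return is the treated arm's, and section 3.5 links self-reported AEs to the months on the device. On this view section 6.5 serves secondary objective 3, and post-operative questioning does not differ by arm. This is plausible and it stands. A reader might take 3 against 0 post-operative months as the plan's settled design, but the documents do not establish that. Table 2 does have a month-3 column, so reading A is possible and no more.

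A reader might also infer that sections 6.1 and 6.5 contradict each other. They need not: a reporting period can outlast active questioning, and section 6.5 itself has all AEs in the study period recorded. That rule does not ensure that anyone asks, and the study period is not defined by arm, but it does narrow the gap.

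Next, both arms receive the follow-up questionnaire at 3, 6 and 12 months after surgery (section 4.4). If that attachment has an AE section, common post-operative questioning already exists. It is not available here, so this remains open.

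Finally, no listed objective compares mild post-operative AEs between arms, and men choose their arm (section 3.5). Both points are fair and limit the severity. They do not remove the comparison that section 5.2 announces.

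**Conclusion.** The point holds in a limited form. On all three readings, the AE comparison in section 5.2 has no window and sets counts that may include 3 to 4.5 months of traction-phase events against control counts that cannot. On the schedule-table reading alone, post-operative questioning is also unequal, at up to 3 months in controls against 0 in treated men.

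The capture gap is confined to milder post-operative events found by asking. Complications under secondary objective 4 are largely unaffected. A reader might infer that controls will appear to have more AEs, or that treated men will. The documents support neither: the direction depends on the reading, and the number of events missed cannot be derived because no AE rates are given. The person-months measure time under questioning, not bias.

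The result rests on the surgery times in Tables 1 and 2 and section 3.5, and on the follow-up questionnaire being unseen. If that questionnaire already asks both arms about AEs, what remains is the missing window in section 5.2. Severity is minor; this is a cheap improvement.

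**What to change.** In section 6.5, replace the single period with two:

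- **Traction phase, treated arm only:** baseline to surgery. Report under secondary objective 3 and leave out of the between-arm comparison.
- **Post-operative phase, both arms:** implantation to 3 months after it, which is the section 6.1 period. Ask the same AE items at the 3-month survey or telephone contact already planned in section 4.4.

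In section 5.2, limit the between-arm AE comparison to that post-operative phase and call it descriptive, since patients choose their arm. Whether it is shown as counts or as the proportion of men with an event is a matter of preference.

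Post-operative questioning then becomes 40 × 3 = 120 person-months in each arm, or 20 × 3 = 60 at the minimum number of completers. The cost is a short edit to each of the two sections and one set of items at an existing contact. No visit is added. The downside is a slightly longer survey, and there is none if the questionnaire already carries the items.

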## **6.6 Reporting of Serious Adverse Events and Unanticipated Problems**

When an adverse event has been identified, the study team will take appropriated action necessary to protect the study participant and then complete the Adverse Event Form. The sponsor-investigator will evaluate the event and determine the necessary follow-up and reporting required.

### **6.6.1 Sponsor-investigator Reporting: Notifying the Mayo IRB**

An adverse event form will be completed for any serious adverse event. This will be reported to the Mayo IRB in a de-identified manner.

The study team will report to the Mayo IRB any UPIRTSOs and Non-UPIRTSOs according to the Mayo IRB Policy and Procedures.

Information collected on the adverse event form (and entered into the research database)

- Subject's ID
- Description of adverse event
- The date the adverse event occurred and resolved (if applicable)
- Intensity
- Outcome
- Action taken to address
- Relationship to study
- Impact on study withdrawal
- Classification as serious or not

The sponsor-investigator will review all adverse event reports to determine if specific reports need to be made to the IRB. The sponsor-investigator will sign and date the adverse event report when it is reviewed. For this protocol, only directly related SAEs/UPIRTSOs will be reported to the IRB.

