## 6 Safety and Adverse Events

### Definition of Adverse Event

Unanticipated Problems Involving Risk to Subjects or Others (UPIRTSO) - any unanticipated problem or adverse event that meets the following three criteria:

Serious: Serious problems or events that results in significant harm, (which may be physical, psychological, financial, social, economic, or legal) or increased risk for the subject or others (including individuals who are not research subjects). These include: (1) death; (2) life threatening adverse experience; (3) hospitalization - inpatient, new, or prolonged; (4) disability/incapacity - persistent or significant; (5) breach of confidentiality and (6) other problems, events, or new information (i.e. publications, interim findings, product labeling change) that in the opinion of the local investigator may adversely affect the rights, safety, or welfare of the subjects or others, or substantially compromise the research data, AND

Unanticipated: (i.e. unexpected) problems or events are those that are not already described as potential risks in the protocol, consent document, not listed in the Investigator's Brochure, or not part of an underlying disease. A problem or event is "unanticipated" when it was unforeseeable at the time of its occurrence. A problem or event is "unanticipated" when it occurs at an increased frequency or at an increased severity than expected, AND

Related: A problem or event is "related" if it is possibly related to the research procedures.

Adverse Event - an untoward or undesirable experience associated with the use of a medical product (i.e. drug, device, biologic) in a patient or research subject.

Serious Adverse Event - adverse events are classified as serious or non-serious. Serious problems/events can be well defined and include:

- Death
- Life threatening adverse experience
- Hospitalization
- Inpatient, new, or prolonged; disability/incapacity
- And/or per protocol may be problems/events that in the opinion of the sponsor-investigator may have adversely affected the rights, safety, or welfare of the subjects or others, or substantially compromised the research data.

All AEs that do not meet any of the criteria for serious, should be regarded as non-serious AEs.

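### Section 6.6.1 sends every SAE form to the Mayo IRB and then limits IRB reports to 'directly related' events, an undefined test narrower than the 'possibly related' tests elsewhere in section 6

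*Combined protocol and SAP*

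**What the plan says.** Section 6.6.1 contains four statements about what goes to the Mayo IRB.

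- It opens: "An adverse event form will be completed for any serious adverse event. This will be reported to the Mayo IRB in a de-identified manner". No relatedness condition is attached.
- It then commits the study team to report UPIRTSOs and Non-UPIRTSOs under Mayo IRB policy.
- After listing the contents of the form, it says: "The sponsor-investigator will review all adverse event reports to determine if specific reports need to be made to the IRB".
- It closes: "For this protocol, only directly related SAEs/UPIRTSOs will be reported to the IRB".

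Section 6.6, whose title covers SAEs, gives a similar discretion: "The sponsor-investigator will evaluate the event and determine the necessary follow-up and reporting required".

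Other parts of section 6 set their own relatedness tests. In the definitions, a UPIRTSO counts as related "if it is possibly related to the research procedures". Section 6.5 says that an SAE after the study period that is "considered to be at least possibly related to the study treatment or study participation will be recorded and reported immediately"; it does not name the recipient. Section 6.6.2 halts the study for IRB re-review when 5 patients have SAEs, and that sentence has no relatedness condition. Under section 6.6.3 the study investigator does the medical monitoring of SAEs.

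**The concern.** A coordinator holding a completed form for an SAE judged possibly but not directly related finds one instruction to send it and another not to. The words 'for this protocol' make the closing sentence look like a study-specific override, so the less protective instruction is the one likely to be followed.

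What is at stake is oversight. The Mayo IRB is the only reviewer of SAEs outside the study team that section 6 names. The sponsor-investigator's judgement of relatedness would decide what the IRB sees, against a test that the protocol does not define. The forms remain in the research database, so no data are lost.

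**Working it through.** No formula decides this point. The check is to set the rules side by side and ask, for each kind of SAE, whether they agree.

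**Step 1. Apply each sentence to each kind of SAE.**

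| SAE | Opening of 6.6.1 | UPIRTSO/Non-UPIRTSO sentence | Close of 6.6.1 |
|---|---|---|---|
| Directly related | report | per IRB policy | report |
| Possibly, not directly, related; unanticipated | report | a UPIRTSO, so reported under policy | not reported, if 'directly related' also governs UPIRTSOs |
| Possibly, not directly, related; anticipated | report | not a UPIRTSO; depends on policy not supplied | not reported |
| Unrelated | report | not a UPIRTSO; depends on policy not supplied | not reported |

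The sentences agree only in the first row.

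**Step 2. Try the generous reading.** The closing phrase can be read so that 'directly related' qualifies SAEs only and every UPIRTSO is still reported. That resolves the second row but not the third or fourth. The third row is a realistic case. Section 3.5 names urethral perforation, corporal perforation, device malfunction, bowel injury and vascular injury, "all of which are standard potential complications of the surgery". By definition, unanticipated "problems or events are those that are not already described as potential risks in the protocol". A serious perforation at expected frequency and severity is therefore not unanticipated and not a UPIRTSO.

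**Step 3. Compare the thresholds.** 'Directly related' is narrower than 'possibly related' (UPIRTSO definition) and 'at least possibly related' (section 6.5). Sections 6.3 and 6.6.2 use a test of reasonable relation, and section 6.4 uses plain 'related'. How far 'directly' departs from those three is a matter of interpretation, because it is undefined. The conflict with the two 'possibly' tests does not depend on that.

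**Step 4. Is deleting the closing sentence enough?** No. The review sentence in 6.6.1 and the last sentence of 6.6 would still let the sponsor-investigator decide which reports go to the IRB, without excepting SAEs.

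**Step 5. Extra forms if all SAEs are reported.** The documents give no SAE rate, so these are assumptions: SAE risk p of 2.5%, 5% or 10% per man; a share q of 20%, 50% or 80% of SAEs not directly related; one SAE per affected man; independent risks; and all 80 men accrued (section 3.4). The baseline for comparison is full adherence to the closing sentence, with nothing reported by the policy route.

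Ignoring the halt, extra forms = 80 × p × q. This runs from 80 × 0.025 × 0.2 = 0.4 to 80 × 0.10 × 0.8 = 6.4.

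The halt in 6.6.2 caps affected patients at 5 unless the IRB allows resumption. With X binomial(80, p), extra forms up to the halt = q × E[min(X, 5)].

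| p | 80p | P(X ≥ 5) | E[min(X, 5)] | Extra forms at q = 0.2 / 0.5 / 0.8 |
|---|---|---|---|---|
| 2.5% | 2 | 0.05 | 1.98 | 0.4 / 1.0 / 1.6 |
| 5% | 4 | 0.37 | 3.61 | 0.7 / 1.8 / 2.9 |
| 10% | 8 | 0.91 | 4.86 | 1.0 / 2.4 / 3.9 |

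The range is 0.4 to 3.9 forms. The uncapped 6.4 is unrealistic, since at 10% risk the halt would be reached with probability 0.91.

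**The case against.** The strongest reply is that Mayo IRB policy governs in any case. Section 6.6.1 separately promises to report UPIRTSOs and Non-UPIRTSOs under that policy, which may capture some or all of the SAEs in question. This stands as a limit on the consequence: a reader might infer that the IRB would learn of possibly related SAEs only once five patients are affected, and the documents do not support that. It does not remove the contradiction, because a cited policy cannot make two opposite instructions in one section both followable.

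A second reply is that the sponsor may have intended the narrower rule. The documents do not show which sentence was meant. One of them must change either way, and 'directly related' would still disagree with the two 'possibly related' tests.

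Three further inferences go beyond the text.

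- Up to four patients could have SAEs before the halt, and one might say that the opening sentence puts all four forms before the IRB and the closing sentence none. The opening sentence gives no deadline, so nothing shows that the forms would arrive before a fifth case. 'None' is also only the extreme in which no SAE is judged directly related.
- An SAE might stop a patient's therapy under 6.6.2 as reasonably device-related and yet go unreported as not directly related. That needs a distinction between the two terms which the protocol never draws.
- Section 8.2 says that a Primary Investigator invented the device. The documents do not state that this person is the sponsor-investigator who judges relatedness.

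**Conclusion.** The contradiction is certain on the current text, and no other section reconciles it. The consequence is conditional. If staff follow the closing sentence, SAEs judged possibly but not directly related may not reach the IRB, unless policy on UPIRTSOs and Non-UPIRTSOs captures them or the halt is reached. How many would be missed cannot be determined from the documents. The point concerns safety oversight alone; sample size and the primary length comparison are untouched. It should be corrected because the repair is small, restores a commitment that the section already makes, and lets the IRB see the same SAEs that count toward the halt.

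**What to change.** Preferred change:

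- In 6.6.1, delete the closing sentence. Keep the opening any-SAE sentence and the sentence on UPIRTSOs and Non-UPIRTSOs. The latter is still needed, because the UPIRTSO definition of serious includes items, such as breach of confidentiality, that the SAE list does not name.
- In 6.6.1, reword the review sentence so that the sponsor-investigator reviews every report but decides on IRB reporting for non-serious events only.
- In 6.6, limit the discretion over reporting to non-serious events in the same way, and refer to 6.6.1 for SAEs.
- Leave the five-patient halt in 6.6.2 as it is; its wording already counts all SAEs.

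If the sponsor intended a relatedness limit, the minimum is to replace 'directly related' with 'at least possibly related' and give the opening sentence the same scope. That removes the contradiction, but unrelated SAEs that count toward the halt would not be reported under this rule.

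The preferred change deletes one sentence and rewords two. It adds no data collection, since a form is already completed for every SAE. The IRB receives a few more forms, including some for SAEs unrelated to traction and some for control patients. Section 6.4 already excludes uneventful elective admissions for a preexisting condition, so routine implant stays should not add to the count.
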